6.3.2 Brief Physical Examination

A brief physical examination will include, at a minimum, assessments of the skin, lungs, CV system, and abdomen (liver and spleen). Assess for changes in onset of menses (female participants) or sexual activity (male or female participants). Determine if there is a need for contraception or barrier use. Height and weight will be measured at Screening only. Investigators should pay special attention to clinical signs related to previous serious illness.

6.3.3 Vital Signs

Vital signs will be measured before blood collection for clinical laboratory assessments and PK analysis (where applicable) and will include measurements of systolic and diastolic blood pressure, pulse rate, and body temperature. Subjects should be in a seated position for at least 5 minutes before vital signs measurement.

6.3.4 Clinical Safety Laboratory Assessments

All protocol-required laboratory assessments must be conducted in accordance with the Study Reference Manual or Laboratory Manual and the protocol Schedule of Assessments ([Table 1](#)). Laboratory requisition forms must be completed, and samples must be clearly labeled with the subject number, protocol number, site number, and visit date. Details for the preparation and shipment of samples will be provided by the laboratory and are detailed in the Study Reference Manual or the Laboratory Manual. Reference ranges for all safety parameters will be provided to the site by the laboratory responsible for the assessments.

A list of clinical laboratory tests and parameters is provided in [Table 4](#).

All laboratory tests with values that are considered clinically significantly abnormal during participation in the study should be repeated until the values return to normal or baseline. If such values do not return to normal within a period judged reasonable by the Investigator, the etiology should be identified, if possible, and the Sponsor and Medical Monitor notified.

Table 4: Laboratory Tests

Diagnostic Screening Tests		

• HBsAg• Hepatitis C antibody• Anti-HBc• Anti-HBs^a		

• Pregnancy tests: (serum at Screening and urine at other visits when performed; women of CBP only)^b• FSH (as needed in women of non-CBP only)• At the Investigator's discretion, subjects may be screened for alcohol and illicit drug use.		
Serum Chemistry		

• BUN• Creatinine• Glucose (fasting not required)• Sodium• Potassium• Chloride	
• Total carbon dioxide• Calcium• AST• ALT• Alkaline phosphatase	
• Uric acid• Total bilirubin (+fractionated if required)• Total protein• Albumin
Hematology		

• Platelet count• RBC count• WBC count (absolute)• Hemoglobin• Hematocrit	
• RBC Indices:
• MCV• MCH• MCHC• Reticulocyte percentage	
• WBC Differential:
• Neutrophils• Lymphocytes• Monocytes• Eosinophils• Basophils
Urinalysis		

• Specific gravity• Microscopic examination (if blood or protein is abnormal)		
• Dipstick: pH, Glucose, Protein, Blood Ketones

a. Reflex test: a negative HBsAg and a positive anti-HBc may enroll if there is a positive anti-HBs demonstrating natural immunity

b. Pregnancy tests should be administered based on CBP, which may change after the start of the study (e.g. a premenarchal female subject experiences menarche or a female subject ceases to meet the criteria of CBP)

ALT = alanine aminotransferase; Anti-HBc = anti-hepatitis B core antigen; Anti-HBs = anti-hepatitis B surface antigen; AST = aspartate aminotransferase; BUN = blood urea nitrogen; CBP = child-bearing potential; FSH = follicle-stimulating hormone; HBsAg = hepatitis B surface antigen; MCH = mean corpuscular hemoglobin; MCHC = mean corpuscular hemoglobin concentration; MCV = mean corpuscular volume; RBC = red blood cell(s); WBC = white blood cell(s).

6.3.5 Electrocardiograms

Single 12-lead ECGs will be obtained at a subset of sites in a subset of subjects at timepoints indicated in the Schedule of Assessments ([Table 1](#)) and Section 7 using an ECG machine that automatically calculates the heart rate and measures PR, QRS, QT, and QTc intervals. Subjects should be in a supine or semi-supine position for at least 5 minutes before ECG is measured. In case of an abnormal ECG or excess artifact, the ECG may be repeated two additional times over several minutes (triplicate in total), to allow further evaluation and averaging of interval measurements as necessary. Abnormal ECGs should be characterized as clinically or non-clinically significant by the investigator. In the event of a clinically significant change from baseline in the ECG for which the etiology cannot be identified, the Medical Monitor should be contacted.

6.3.6 Local Tolerability Scale

6.3.6.1 Investigator-Assessed Local Tolerability Scale

At each specified study visit, the Investigator (or qualified evaluator) will assess the presence and overall degree of irritation at the application sites, according to a 5-point LTS. The score will ideally represent an “average” across all application sites. To the fullest extent possible, the same Investigator (or designated evaluator) will perform all tolerability assessments for an individual subject throughout the study. If the subject is applying study drug to “sensitive areas”, a separate LTS will be used to assess the degree of irritation for each of these areas where study drug is applied. The sensitive areas that will be assessed are face, neck, skin folds, axilla, inframammary, anal crux, and genitalia. An example of the Investigator-assessed LTS is shown in [Appendix 15](#). The LTS should be completed pre-dose at Baseline and within 2 hours post-dose at Weeks 1, 2 and 4. At Week 8 and the ET visit, when study drug is not being applied at that visit, the LTS should be completed when other assessments are completed. Other than at the Baseline visit, the Investigator-assessed LTS should only completed when the subject is currently receiving study drug (i.e. has applied at least one application in the last 48 hours).

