m. If needed, laboratory testing at the Follow-up visit for ongoing AEs or abnormal laboratory values.

n. Urine sample collection for urinalysis is not required at the Baseline Visit if it has been \leq 14 days since samples were collected at Screening and the results of those analyses were not clinically significant.

o. Blood sample for PK will be collected in a subset of subjects. Sample to be collected prior to study drug application in clinic. Informed consent/assent will be required.

p. Photography will be performed in a subgroup of subjects at selected study sites. Informed consent/assent and photographic release will be required.

q. The vIGA-ADTM assessment should be performed before the %BSA and EASI assessments. The subject's scalp should be excluded from the vIGA-ADTM, %BSA, and EASI calculations.

r. The LTS assessment consists of an Investigator-assessed and a subject (or caregiver)-assessed component. Both the Investigator-assessed LTS and subject (or caregiver)-assessed LTS should be completed within 2 hours post-dose at Weeks 1, 2 and 4. At Week 8 and the ET visit, when study drug is not applied, the LTS should be completed when other assessments are completed. If the subject (or caregiver) is applying study drug to "sensitive areas" (face, neck, skin folds, axilla, inframammary, anal crux, and/or genitalia), the Investigator will also complete a separate LTS assessment for each sensitive area where study drug is being applied.

s. Subjects (or Caregivers) should perform the PP-NRS assessment daily and record the results in their diary. When subjects dose in the clinic on study visit days, subjects will not complete the diary at home; application time and PP-NRS will be recorded in the clinic.

t. Subjects will be instructed on when and how to complete diaries.

u. Subjects will be instructed to apply study drug QD at the approximate same time each day, based on subject preference.

v. At clinic visits, study drug will be applied after safety and efficacy assessments have been conducted (except for LTS at Weeks 1, 2 and 4).

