6.3.6.2 Subject (or Caregiver)-Assessed Local Tolerability Scale

At each specified study visit, the subject or caregiver will separately assess the presence and degree of burning/stinging and itching at the application sites, each according to a 5-point LTS. The subject or caregiver will not score each sensitive area individually but provide one overall score that will ideally represent an “average” across all application sites. An example of the subject (or caregiver)-assessed LTS is shown in [Appendix 16](#). The subject (or caregiver)-assessed LTS should be completed pre-dose at Baseline and within 2 hours post-dose at Weeks 1, 2 and 4. At Week 8, when study drug is not being applied at that visit, the LTS should be completed when other assessments are completed. Other than at the Baseline visit, the subject (or caregiver)-assessed LTS should only completed when the subject is currently receiving study drug (i.e. has applied at least one application in the last 48 hours). For subjects ages < 12 years, the LTS will be completed by the caregiver. For subjects ages ≥ 12 years, the LTS will be completed by the subject.

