8.1.3 Adverse Events of Special Interest

In prior clinical studies, contact dermatitis, folliculitis, and headache have been identified as AEs of particular clinical importance and will be reported as AESIs in this study whether or not the AE is considered related to study drug.

In each case study drug may be continued or discontinued, based on Investigator judgment, and may be restarted when the event resolves. In addition, the following information must be collected for each of these AESIs:

Contact Dermatitis

The study site should collect location, duration, size, associated symptoms (itching, burning, pain), severity (mild, moderate, severe), time to onset, and photograph the affected site (if possible). If the subject or caregiver contacts the study site to report significant skin irritation at or near the site of study drug application between study visits, the subject should be brought in for an unscheduled visit, if possible.

Headache

The study site should collect duration, severity (mild, moderate, severe), time to onset, and location (e.g., frontal, temporal, occipital, diffuse).

Follicular Event

The study site should collect the location, duration, size, associated signs and symptoms (itching, burning, pain, erythema), severity (mild, moderate, severe), describe morphology [scale (keratotic/cornified) or no scale (non-keratotic/non-cornified)], time to onset, and photograph the affected site (if possible). Additional information regarding management of folliculitis is provided in Section 8.2.1.2.4.

In particular, the term 'folliculitis' may not correctly describe the morphology of the observed local follicular events as these appear to be more consistent with a keratoses pilaris-like follicular based papule. Tapinarof upregulates components of the stratum corneum, including involucrin, hornerin, and filaggrin and increased cornification at, and subsequent mechanical occlusion of, the follicular ostia has been suggested to be a potentially on target mechanism by which these lesions may develop in some individuals treated with tapinarof cream. Additional morphologic description will help to more fully and appropriately characterize these follicular events.

Possible descriptors include, but are not limited to:

- Folliculitis
 - Non-inflammatory
 - Inflammatory
- Milia
 - Non-inflammatory
 - Inflammatory
- Keratosis pilaris

- Non-inflammatory
- Inflammatory

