8.2.1.2.4 Folliculitis

Subjects using tapinarof topically may experience folliculitis. The majority of these events are mild or moderate and do not require intervention or interruption in study drug use. On close inspection, the morphology is similar to that of keratosis pilaris suggesting that the potential mechanism may be increased follicular cornification with subsequent follicular plugging. Importantly, AhR regulates the epidermal differentiation complex and tapinarof has been shown to repair the skin barrier through activation of stratum corneum components including fillagrin, hornerin and involucrin. This latter point suggests that the keratosis pilaris-like reaction may be an on-target effect associated with a therapeutic response to tapinarof cream.

While the majority of events have not required nor resulted in the need for intervention, several approaches can be employed to manage those patients with folliculitis who may be symptomatic including temporary interruption of study drug use at sites of folliculitis and/or the local application to affected areas of topical keratolytics such as 12% lactic acid lotion or 5-10% urea creams or lotions.

8.2.1.2.5 Other Management Criteria:

The Medical Monitor should be notified if any of the following occur:

- Severe signs or symptoms, or significant changes in any of the safety assessments, that put the safety of the subject at risk (e.g., laboratory tests or vital signs, etc.) as judged by the Investigator.

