The imputation models may be modified based on the actual data if there is an issue in model convergence.

Sensitivity analyses of the primary and secondary endpoints will be performed using MI (non-estimand), last observation carried forward (LOCF), observed cases (OC) (i.e., no imputation), and imputing missing data as Treatment Failures (TF). Only missing data up to Week 8 will be imputed. Missing data at the Week 9 Follow-up visit will be summarized as OC only.

LOCF: The last observed value will be carried forward for any subsequent missing values. Baseline values will not be carried forward. Unscheduled visits will be included.

TF: missing data will be imputed as treatment failures for responder endpoint.

Missing functional outcomes, quality of life endpoints or safety endpoints will not be imputed.

Average weekly PP-NRS scores will be calculated for all nominal visits as the average of 7 daily post-baseline PP-NRS scores prior to and including the values assessed on the visit date. If daily PP-NRS scores are missing for more than 3 days in a 7-day period, the average weekly PP-NRS score will be set to missing. If two or more scores are reported on the same day, the maximum score on that day will be used.

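### Post-baseline local tolerability scores require recent application, so subjects and skin areas taken off drug for irritation can drop out of the LTS tables, and each arm is likely to look better tolerated than it was

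*Protocol*

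**What the plan says.** Section 2 of the Protocol lists mean LTS by visit as a safety endpoint: the investigator's form overall and for sensitive areas, and the subject or caregiver form overall.

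**Completion rule.** Section 6.3.6.1 states that, apart from Baseline, the investigator's form "should only completed when the subject is currently receiving study drug (i.e. has applied at least one application in the last 48 hours"). Section 6.3.6.2 repeats the condition: "Other than at the Baseline visit, the subject (or caregiver)-assessed LTS should only completed when the subject is currently receiving study drug". No other visit is exempt. For sensitive areas, footnote r of Table 1 says "the Investigator will also complete a separate LTS assessment for each sensitive area where study drug is being applied".

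**Early Termination.** Section 6.3.6.1 also says "At Week 8 and the ET visit, when study drug is not being applied at that visit, the LTS should be completed" alongside the other assessments. Footnote r and section 7.9 schedule both forms at ET. Section 6.3.6.2 mentions only Week 8 at this point. Sections 4.6.2 and 7.9 set no limit on the time between last application and the ET visit.

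**Stopping and pausing.** Section 4.6.1 withdraws subjects for certain drug-related adverse events. For the events of special interest, which include contact dermatitis and folliculitis, section 8.1.3 says: "In each case study drug may be continued or discontinued, based on Investigator judgment, and may be restarted when the event resolves". Section 8.2.1.2.4 mentions "temporary interruption of study drug use at sites of folliculitis".

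**Analysis.** SAP 13.3 summarizes LTS scores and changes from baseline by treatment and visit, and by area for sensitive sites. SAP 10.4 states: "Missing functional outcomes, quality of life endpoints or safety endpoints will not be imputed".

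**The concern.** Whether a score is recorded can depend on how bad the score would have been. Appendix 15 defines investigator score 2 as irritation that needs no change of treatment, which implies that such changes are to be expected mainly at 3 and 4. Stopping or pausing is such a change, and after 48 hours it switches the assessment off. The scores most likely to lead to stopping are then the ones most likely to go unrecorded.

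At stake is the tolerability description of a cream that may be applied to the face, skin folds and genitalia. Neither section 2 nor SAP 13.3 says that the mean is conditional on continued application, so a reader of the tables would take it as describing everyone treated.

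**Working it through.** The plan gives no LTS figure to reproduce. Its 97.2% power concerns the primary endpoint and plays no part here. The check is first of the rules, then of the possible size.

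**1. Who is lost under the rules as written**

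- *Stopped for irritation, ET visit more than 48 hours after the last application.* The LTS is scheduled, but the 48-hour condition says not to complete it. The instructions conflict.
- *Paused for more than 48 hours and still off drug at Week 1, 2 or 4.* No LTS.
- *Paused, but resuming at the Week 1, 2 or 4 visit.* Drug is applied in clinic and the LTS follows within 2 hours, so the score is recorded.
- *Paused for more than 48 hours at Week 8.* No application takes place at that visit, so nothing restores the score. No LTS is scheduled between Weeks 4 and 8, and the Week 6 contact is a phone call without one. Irritation that arises and leads to stopping in that interval may never be scored.
- *Paused at one sensitive area only.* The subject still meets the 48-hour condition and the overall score is kept. That area's score is lost through the separate wording on where drug is applied.

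**2. Effect on an arm's mean**

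Let q be the share of the arm unscored at a visit because drug was stopped or paused for irritation, m1 their mean on-drug score, and m0 the mean among those still applying.

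- Reported mean = m0
- Full-arm mean = (1 − q) × m0 + q × m1
- Understatement = q × (m1 − m0)

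This is downward whenever those who stopped were more irritated than those who stayed. The documents give none of the three inputs. Assumed: m0 = 0.4, m1 from 1 to 3, q from 1% to 15%. The upper end equals the 15% all-cause tapinarof loss in section 10.2, and is not an irritation rate. Full-arm means, against a reported 0.40:

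| q | m1 = 1 | m1 = 2 | m1 = 3 |
|---|---|---|---|
| 1% | 0.406 | 0.416 | 0.426 |
| 2% | 0.412 | 0.432 | 0.452 |
| 5% | 0.43 | 0.48 | 0.53 |
| 10% | 0.46 | 0.56 | 0.66 |
| 15% | 0.49 | 0.64 | 0.79 |

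The understatement runs from 0.01 × (1 − 0.4) = 0.006 to 0.15 × (3 − 0.4) = 0.39.

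**3. Effect on the frequency table**

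Assume 3% of those still applying, and all who stopped, score 2 or more. The full-arm share is 0.99 × 3% + 1% = 4.0% at q = 1%, and 0.85 × 3% + 15% = 17.6% at q = 15%, against a reported 3%.

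**4. Between-arm contrast (full-arm minus reported), with m1 = 2 and m0 = 0.4**

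- 5% tapinarof, 2% vehicle: 1.6 × (0.05 − 0.02) = +0.048
- Equal shares: 0
- 2% tapinarof, 5% vehicle: −0.048

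Section 10.2 does not settle the sign. Its all-cause losses are 15% of 267 = 40 and 30% of 133 = 40 subjects, with no split by reason.

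**5. Would pooling off-drug scores cure it?**

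No. If irritation has settled to 0 by the visit, then at q = 5% the pooled mean is 0.95 × 0.4 + 0.05 × 0 = 0.38, which is below 0.40.

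**The case against.** The best defence is that the LTS is an on-treatment measure. It rates irritation at application sites, within 2 hours of dosing at Weeks 1, 2 and 4, and a subject off drug has no such window. That is a legitimate target and a reason to keep the on-drug table. It does not excuse leaving the condition unstated in the endpoint and the SAP, or the conflict at ET.

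The second defence is that the events are captured elsewhere. Section 8.1.3 requires detailed data on contact dermatitis and follicular events. SAP 13.2 tabulates events leading to drug discontinuation, summarizes the most extreme level of each special-interest event, and plots time to first event. This stands, and it limits harm to the overall safety conclusion. It does not repair the LTS tables.

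Third, a reader might infer that every bad score is lost for good. The documents do not support that. Scores before stopping stay in their own visits. Section 8.1.3 asks for an unscheduled visit, if possible, when significant irritation is reported, and section 7.10 allows both LTS forms there. The offset is partial: the 48-hour condition has no exemption for such visits, and SAP section 7 takes the visit nearest the target day, not the worst score.

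Finally, off-drug scores can mislead. Erythema, peeling and itching overlap with atopic dermatitis itself, so a late score may reflect untreated disease. This stands, and it is why such scores should not enter the on-drug mean.

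**Conclusion.** The concern holds for each arm taken separately. The 48-hour condition, and the sensitive-area wording beside it, can remove scores because of the irritation they would have measured. No planned LTS analysis offsets this, and the rule contradicts the scheduled ET assessment. Each arm's LTS results are likely to look better than the truth, provided that those who stop for irritation score higher than those who continue.

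The size is unknown. The range of 0.006 to 0.39 points rests wholly on assumed stopping rates and scores. At small stopping rates the shift in the mean is modest, and the loss from the upper score categories matters more.

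A reader might infer that the comparison is tilted toward tapinarof. The documents do not support that: they give no irritation-related stopping rate by arm, the sign can go either way, and no formal safety comparison is planned. Nor is the absence of imputation for safety data a fault in itself. The point deserves correction but does not touch efficacy or, on its own, overturn the safety evaluation.

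**What to change.** **Protocol 6.3.6.1, 6.3.6.2, footnote r and 7.9.** Reconcile the 48-hour condition with the ET schedule. Complete both LTS forms at scheduled visits and at ET regardless of time since last application, including every sensitive area treated at any time since Baseline. Name ET in 6.3.6.2 as well. Record the date of last application, overall and for any paused area, so that off-drug scores can be flagged.

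**SAP 13.3.** Keep the by-visit table restricted to on-drug scores as the main display, and label it so. Add:

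- a table of all assessed subjects;
- the worst post-baseline LTS per subject and area, including unscheduled and ET visits;
- counts by arm and visit of LTS that were off-drug, or not done because drug was stopped or paused, with the reason.

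**Cost.** Wording in both documents, a last-application date and a reason field on the CRF, and a few tables. The scale, staff and visits are already in place. The downside is that off-drug scores may have settled or may reflect the underlying disease, so they are shown separately and kept out of the on-drug mean.

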6.3.6.2 Subject (or Caregiver)-Assessed Local Tolerability Scale

At each specified study visit, the subject or caregiver will separately assess the presence and degree of burning/stinging and itching at the application sites, each according to a 5-point LTS. The subject or caregiver will not score each sensitive area individually but provide one overall score that will ideally represent an “average” across all application sites. An example of the subject (or caregiver)-assessed LTS is shown in [Appendix 16](#). The subject (or caregiver)-assessed LTS should be completed pre-dose at Baseline and within 2 hours post-dose at Weeks 1, 2 and 4. At Week 8, when study drug is not being applied at that visit, the LTS should be completed when other assessments are completed. Other than at the Baseline visit, the subject (or caregiver)-assessed LTS should only completed when the subject is currently receiving study drug (i.e. has applied at least one application in the last 48 hours). For subjects ages < 12 years, the LTS will be completed by the caregiver. For subjects ages ≥ 12 years, the LTS will be completed by the subject.

